6.1.3.1 Model checking procedures

Missing data will be assumed to be missing at random and thus the above analysis will be performed on all available data. There will be no imputation of missing data.

Normal distribution of UGE24 will be examined. In case there is strong deviation from normal distribution, a supportive analysis, similar to the primary UGE analysis, except that natural logarithm of the ratio to baseline in UGE24 will be modeled instead of the change from baseline, and baseline fasting plasma glucose will also be log transformed. For this analysis, the least-square geometric mean will be estimated for each diabetic status by renal function by day combination, in addition to the geometric mean ratio of each renal impaired group to the group with normal renal (or other least severe group with data) function and the corresponding two-sided 90% confidence interval and p-value, separately for each diabetic status by day combination.

[figure not shown]
In addition, another supportive analysis similar to the primary UGE analysis, except that baseline UGE24 will be used as a covariate in place of baseline fasting plasma glucose. Baseline UGE24 will be the collection taking place on Day -1. The same model-based quantities described for the primary analysis will be extracted.

[figure not shown]
Same analysis, for both supportive analysis models, will be repeated for overall diabetic status, without including the interaction of renal function*diabetic status.

[figure not shown]

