Data analysis	The primary analyses will assess the effect of reduced renal function on 24-hour urinary glucose excretion (UGE24) and on the PK of LIK066. The change from baseline in UGE24 will be analyzed using an analysis of covariance model with diabetic status, renal impaired group, day, and all associated interactions (where possible) as fixed factors and age, baseline body weight, and baseline fasting plasma glucose as covariates. Each of the log-transformed PK parameters will be analyzed using the same model but without the baseline covariates.
Key words	Decreased renal function. Urinary glucose excretion. Pharmacokinetics

1 Introduction

[figure not shown]
[figure not shown]
Obesity has become a major global health problem that contributes causally to and exacerbates many serious co-morbidities including hypertension, dyslipidemia, and importantly type 2 diabetes (T2DM). In contrast to the numerous medicines that are available to treat these obesity-related diseases, relatively few agents are available for the treatment of obesity itself that are effective, safe or scalable to the size of the affected population (Morgen and Sorensen 2014). A novel mechanism to lower body weight is via inhibition of the sodium glucose co-transporters 1 and 2 (SGLTs) resulting in inhibition of the glucose absorption in the gut and reabsorption in the kidney (Chao and Henry 2010). In healthy subjects, virtually all of the filtered glucose is reabsorbed into the circulation and no glucose is detected in the urine. SGLT2 located in the segments 1 and 2 of the proximal tubule contributes to ~90% of reabsorption of the filtered glucose (Abdul-Ghani et al 2015). SGLT1 is located in the more distal part of the proximal tubule, segment 3, and contributes to the remaining ~10% of filtered glucose. However, when SGLT2 is inhibited with empagliflozin (a SGLT2 inhibitor), SGLT1 compensates for the reabsorption of filtered glucose and SGLT1 is capable of reabsorbing >40% of filtered glucose load in a mouse model (Abdul-Ghani et al 2015). In addition to expression in the kidney, SGLT1 is also expressed in the small intestine, where it is required for glucose and galactose absorption. Inhibition of enteric SGLT1 results in glucose and galactose malabsorption (Turk et al 1991), which results in calorie wasting and other potential endocrine-based weight loss mechanisms.

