3.1 Study design

This study employs an open-label, multiple-dose, parallel-group design in patients with varying degrees of decreased renal function (mild, moderate and severe renal impairment) and subjects with normal renal function. The most common cause of chronic kidney disease is diabetes, which accounts for roughly 50% of all cases. Approximately 50% of the patients enrolled in each group of the mild, moderate and severe renal impairment are expected to be patients with T2DM.

Each subject will participate in a screening period of up to 28 days, one baseline period, one treatment period of 7 days (including domicile and outpatient visits), a follow-up period, and an end-of-study evaluation approximately 96 hours after the last drug administration.

Ten (10) subjects each with mild (eGFR 60-89 ml/min/1.73 m²), Grade A moderate (eGFR 46-59 ml/min/1.73 m²), Grade B moderate (eGFR 30-45 ml/min/1.73 m²), and normal renal function (eGFR ≥90 ml/min/1.73 m²); and up to 10 patients with severe renal impairment (eGFR ≤29 ml/min/1.73 m², not on dialysis) will be enrolled.

Figure 3-1 Study design

Patients with varying degrees of decreased renal function will be enrolled first; subjects with normal renal function will be enrolled after approximately 50% of the patients with decreased renal function (at least two in each group of patients with moderate renal impairment, and at least one patient in the group of patients with severe renal impairment) have been enrolled. Because body weight and age are covariates in the estimation of eGFR formula, the 10 subjects with normal renal function will be matched to 10 of the enrolled patients with

decreased renal function by age (approximately ± 10 years), weight (approximately $\pm 20\%$), and, if possible, diabetic status. The 10 patients with decreased renal function on whom the matching will be based will be selected so as to cover as broad age range as possible. The enrolled patients will be ranked by age and selected, beginning with the youngest and ending with the oldest, in an increment that yields 10 total patients. Efforts will be made to match the diabetic status, where possible, to ensure representation of both diabetic and non-diabetic populations in the group of subjects with normal renal function.

The renal function (eGFR) will be assessed based on the MDRD equation ([Levey et al 2006](#)) during the screening visit. The MDRD equation (Serum creatinine levels in mg/dl) to be used is as follows:

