3.2 Rationale of study design

[figure not shown]
[figure not shown]
The design of this study addresses the primary objective of assessing the effects of LIK066 on urinary glucose excretion and the pharmacokinetics of LIK066 in subjects with reduced renal function as compared to those with normal renal function. The 24-hour urinary glucose excretion (UGE24) is zero in healthy subjects and ~10 g in patients with T2DM in the absence of a SGLT inhibitor such as LIK066. The UGE24 is ~100 g when LIK066 is given to patients with T2DM, therefore, the diabetic status is expected to have little impact on the assessment of UGE24. In addition, the assessment of UGE24 will be based on the changes corrected by baseline UGE24. The matching of subjects with normal renal function to a subset of the subjects with reduced renal function will be done to minimize bias in the comparison due to confounding factors of age, body weight, and diabetic status. An open-label design without a placebo comparator is appropriate as the primary endpoints, 24-hour urinary glucose excretion and pharmacokinetics, are objective parameters.

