11.4.2 Statistical model, hypothesis, and method of analysis

The primary analyses will assess the effect of reduced renal function on UGE24 and on the PK of LIK066.

UGE24

The change from baseline in UGE24 will be analyzed using an analysis of covariance (ANCOVA) model with diabetic status, renal impaired group, day, and all associated interactions (where possible) as fixed factors and age, baseline body weight, and baseline fasting plasma glucose as covariates. Baseline fasting plasma glucose and baseline body weight will be the measurements on Day 1 0-hour. An unstructured covariance matrix will be used.

The least-square mean change from baseline will be estimated for each diabetic status by renal function by day combination. In addition, the mean difference between each renal impaired group and the group with normal renal function and the corresponding two-sided 90% confidence interval and p-value for the difference will be extracted for each diabetic status by day combination.

UGE24 will be summarized by diabetic status, renal function, and day. The change from baseline and % change from baseline will also be summarized.

The relationship between eGFR and UGE24 will be assessed graphically, separately by day.

PK

Each of the log-transformed PK parameters (C_{max} , AUC_{tau} , AUC_{last} , AUC_{inf} as applicable) will be analyzed using the same model described above for UGE24 but without the baseline covariates. For each parameter, the least-square geometric mean will be estimated for each diabetic status by renal function by day combination. In addition, the geometric mean ratio of each renal impaired group to the group with normal renal function (expressed as a percent relative difference) and the corresponding two-sided 90% confidence interval and p-value for the ratio will be extracted for each diabetic status by day combination.

Statistical analysis may be performed to compare the free fraction (f_u) across the treatment groups. If statistically significant difference exists in f_u across treatment groups, the same analysis (as planned for total parameters) will also be performed to compare the AUC_{u} and $C_{max,u}$ between treatment groups.

The summary of PK parameters is described below in [Section 11.4.4](#).

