11.4.3 Handling of missing values/censoring/discontinuations

All drug concentrations below the lower limit of quantification (LLOQ) will be reported as “zero” and will be treated as zero for calculation of PK parameters. No other imputation of missing values will be performed.

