11.4.5 Sensitivity analyses

Two sensitivity analyses of UGE24 may be performed:

(1) a similar analysis as the primary UGE analysis, except that natural logarithm of the ratio to baseline in UGE24 will be modeled instead of the change from baseline. For this analysis, the least-square geometric mean will be estimated for each diabetic status by renal function by day combination, in addition to the geometric mean ratio of each renal impaired group to the group with normal renal function (expressed as a percent relative difference) and the corresponding two-sided 90% confidence interval and p-value, separately for each diabetic status by day combination.

(2) the same analysis described for the primary UGE analysis, except that baseline UGE24 will be used as a covariate in place of baseline fasting plasma glucose. Baseline UGE24 will be the collection taking place on Day -1. The same model-based quantities described for the primary analysis will be extracted.

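### The supportive log-ratio analysis of UGE24 (SAP 6.1.3.1) has no value at a zero baseline, and the supplied text gives no zero or LLOQ rule for urinary glucose (minor)

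*SAP*

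**What the plan says.** SAP 6.1.3.1 describes two supportive analyses of UGE24. The first is triggered by a strong departure from normality. In it the "natural logarithm of the ratio to baseline in UGE24 will be modeled instead of the change from baseline", and fasting plasma glucose is also log-transformed. Geometric means and between-group geometric mean ratios are required for every cell of diabetic status, renal function group and day, and the analysis is repeated with the diabetic strata combined. The second supportive analysis keeps the change from baseline and uses baseline UGE24 as a covariate. SAP 6.1.2 fixes baseline as Day -1. Protocol 11.4.5 lists the log-ratio model as optional: "a similar analysis as the primary UGE analysis, except that natural logarithm of the ratio to baseline in UGE24 will be modeled".

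On baseline values, Protocol 3.2 gives the 24-hour excretion ("UGE24) is zero in healthy subjects and ~10 g in patients with T2DM in the absence of a SGLT inhibitor"). Protocol section 1 says that in healthy subjects "virtually all of the filtered glucose is reabsorbed into the circulation and no glucose is detected in the urine".

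On who is enrolled, Protocol 3.1 says of the renally impaired groups: "Approximately 50% of the patients enrolled in each group of the mild, moderate and severe renal impairment are expected to be patients with T2DM". Of the normal-function group it says: "Efforts will be made to match the diabetic status, where possible, to ensure representation of both diabetic and non-diabetic populations".

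On low values, the rule in Protocol 11.4.3 begins "All drug concentrations below the lower limit of quantification (LLOQ) will be reported as" and goes on to zero. It concerns drug concentrations, as do the LLOQ provisions in Protocol 11.4.4 and SAP 5.2. Beyond that, Protocol 11.4.3 and SAP 6.1.3.1 exclude imputation of missing data.

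**The concern.** The first supportive analysis is the SAP's stated response if the primary model's normality assumption fails badly, so it should be computable when it is called on. A ratio needs a positive denominator. The plan's own design rationale gives zero as the untreated value in healthy people, and the trial deliberately enrols non-diabetic participants. If their Day -1 values are zero, the outcome does not exist for them. If the values are traces, the ratio is driven by measurement near the assay limit.

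At stake are the non-diabetic estimates in this analysis, the meaning of its combined repeat, and the chance that a floor is picked after the data are seen. Other outputs meet the same zero: the ratio plot in SAP 6.1.3.2, percent change from baseline (SAP 2, SAP 6.1.2, Protocol 11.4.2), and the geometric mean and geometric CV of raw baseline UGE24 (SAP 6.1.2).

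**Working it through.** The plan states no figure for this analysis, so there is none to reproduce. The check is whether the outcome is defined at the plan's own values, and how far an unstated rule could move it.

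**Inputs from the documents**
- Untreated UGE24: 0 g in healthy subjects, about 10 g in T2DM (Protocol 3.2).
- UGE24 on LIK066: about 100 g in T2DM (Protocol 3.2). Its use for other participants below is an assumption.
- Impaired patients: 10 + 10 + 10 + up to 10 = 30 to 40, about half with T2DM (Protocol 3.1).
- At least 8 completers in the mild, moderate and normal groups (Protocol 11.7).

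**Step 1: is the outcome defined?** Outcome = ln(on-treatment UGE24 / baseline UGE24).
- Baseline 10 g: ln(100/10) = 2.30, a ratio of 10 (percent change +900%).
- Baseline 0 g: 100/0 has no finite value, so there is no log ratio and no percent change.

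**Step 2: how many participants could be touched?** Half of 30 to 40 gives about 15 to 20 non-diabetic impaired patients, plus the non-diabetic controls. If all had zero baselines, no non-diabetic estimate could be computed and the combined repeat would contain only T2DM patients. If only some did, participants would be dropped because of their baseline value.

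**Step 3: what if a floor is substituted?** For one participant with 100 g on treatment, assumed floors give:

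| Assumed floor (g) | Ratio | ln ratio |
|---|---|---|
| 1 | 100 | 4.61 |
| 0.1 | 1,000 | 6.91 |
| 0.01 | 10,000 | 9.21 |

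For a cell of n participants with k zero baselines, moving the floor from c1 to c2 multiplies the unadjusted geometric mean ratio by (c1/c2)^(k/n). Assume n = 4 (8 completers, half non-diabetic) and c1/c2 = 0.1/0.01 = 10:
- k = 1: 10^(1/4) = 1.8
- k = 2: 10^(2/4) = 3.2
- k = 4: 10^(4/4) = 10

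The shift cancels between two cells of equal size only if they have the same number of zeros. With 2 of 4 zeros in one and 1 of 4 in the other, the between-group ratio moves by 10^(1/4) = 1.8.

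**Step 4: what stays defined?** The primary outcome is a difference: 100 - 0 = 100 g raises no difficulty. The second supportive model also uses the difference and takes baseline UGE24 as a covariate, where zero is a valid value. T2DM ratios at about 10 g are defined.

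**The case against.** Much of the case on the other side stands.

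- *The analysis is conditional and supportive.* True. The SAP runs it only after strong non-normality, and the protocol makes it optional. This sets the weight of the point.
- *Zero baselines in this trial are not documented.* True. The protocol gives round figures for healthy subjects. The normal-function group is not defined as healthy: Protocol 4.1.3 allows conditions such as diabetes or hypertension. No baseline is given for non-diabetic patients with renal impairment. A reader might infer that the documents establish zero baselines in the non-diabetic strata; they do not. Small positive values would keep the ratio defined but leave it sensitive to noise.
- *A rule may exist elsewhere.* Possible. The SOM, the Data Management Plan and the TFL shells were not available, and parts of the documents are removed or redacted. The gap is in the supplied text only.
- *The SAP foresees an empty reference cell.* It allows the least impaired group with data to replace the normal group. That helps only if some non-diabetic cell has usable baselines.
- *The second supportive model still gives non-diabetic and combined estimates.* True, but it stays on the change scale and so does not answer non-normality.
- *SAP 6.1.2 qualifies its statistics as given where appropriate.* This may let undefined summaries be left out, but it sets no rule and does not reach the model.

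A reader might also infer a definite loss of precision against modelling log on-treatment values. The documents do not support a figure. The 24 g and 98 g in Protocol 11.7 describe the change from baseline at 15 mg in T2DM, not on-treatment values at 50 mg. With log-scale SDs s_on and s_b and correlation r, the log ratio is the more variable only if s_b > 2 × r × s_on. At an assumed r = 0.5 and on-treatment CV of 50%, that needs a baseline CV above 50%. At a baseline CV of 30% the log ratio would be the tighter of the two.

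**Conclusion.** The point holds as a minor one. As written, the log-ratio analysis cannot be computed at a zero baseline and depends on noise or an unstated floor near zero. The supplied text has no rule for this. If the analysis is triggered, non-diabetic estimates could be lost and the combined repeat would rest mainly on T2DM patients. The same gap reaches the ratio plot, percent change, and the geometric statistics of raw baseline UGE24.

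That the ratio fails at zero needs no assumption. How many participants are affected is an inference from the healthy-subject figure. The factors 1.8, 3.2 and 10 are illustrations that rest on assumed floors and 4 participants per cell.

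A reader might infer that the trial's main UGE24 conclusion is in doubt. It is not: the primary change-from-baseline model, the T2DM stratum estimates and the second supportive model are untouched by a zero baseline.

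**What to change.** Before database lock:

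1. Check the SOM, the Data Management Plan and the TFL shells for a rule on zero or unquantifiable urinary glucose. If one exists, cite it in the SAP.
2. In SAP 6.1.3.1, model ln(on-treatment UGE24) in place of the log ratio. Keep the stated factors, age, baseline body weight and log fasting plasma glucose; untransformed baseline UGE24 may be added. Make the same change in the combined repeat. Report between-group geometric mean ratios. State how an on-treatment value below quantification would be handled.
3. Base the SAP 6.1.3.2 ratio plot on that model.
4. Give percent change, and the geometric mean and CV of baseline UGE24, only where baseline is quantifiable, with the number not computable. Apply this to the first interpretable results as well.
5. Record the changes from Protocol 11.4.5 (1) and, for percent change, from Protocol 11.4.2, which now says: "The change from baseline and % change from baseline will also be summarized".

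The cost is SAP wording and minor programming, with no new data. The downside is that the supportive result is no longer a fold-change from baseline. If that is wanted, report it for quantifiable baselines only, with counts, and do not label it as an overall result. Percent change will be incomplete for some non-diabetic participants.

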6.1.3.2 Graphical presentation of results

A bar chart showing the least-square mean and mean difference from normal renal function (or other least severe group with data) with two-sided 90% CI at each day will be generated for change from baseline in UGE24 by renal function group for each diabetic status. In addition, similar plot will be produced for ratio to baseline in UGE24 based on the ratio to baseline analysis.

The relationship between eGFR and UGE24 will be assessed by scatterplots and linear regression line with both diabetic statuses overlaying, separately by day.

7 Statistical methods for safety and tolerability data

All subjects within the safety analysis set will be included in the safety data analysis.

7.1 Variables

Adverse events, vital signs (blood pressure, pulse rate, body temperature), ECG intervals, laboratory measurements, anion gap, urine ketones (dipstick), as well as subject demographics, baseline characteristics, and treatment information.

7.2 Descriptive analyses

Subject demographics and other baseline characteristics

All data for background and demographic variables will be listed by renal function, diabetic status and subject. Summary statistics will be provided by renal function.

Relevant medical history, current medical conditions, results of laboratory screens, drug tests and any other relevant information will be listed by renal function and subject.

Treatment

Data for study drug administration (rescue medication) and concomitant therapies will be listed by renal function and subject.

Vital signs

All vital signs data will be listed by renal function, subject, and visit/time and if ranges are available abnormalities (and relevant orthostatic changes) will be flagged. Summary statistics will be provided by renal function and visit/time.

ECG evaluations

All ECG data will be listed by renal function, subject and visit/time, abnormalities will be flagged. Summary statistics will be provided by renal function and visit/time.

Clinical laboratory evaluations

All laboratory data will be listed by renal function, subject, and visit/time and if normal ranges are available abnormalities will be flagged. Summary statistics will be provided by renal function and visit/time.

Adverse events

All information obtained on adverse events will be displayed by renal function and subject.

The number and percentage of subjects with adverse events will be tabulated by body system and preferred term with a breakdown by renal function. A subject with multiple adverse events within a body system is only counted once towards the total of this body system.

For the legal requirements of ClinicalTrials.gov and EudraCT, two required tables on treatment emergent adverse events which are not serious adverse events with an incidence greater than 1% and on treatment emergent serious adverse events and SAE suspected to be related to study treatment will be provided by system organ class and preferred term on the safety set population.

If for a same patient, several consecutive AEs (irrespective of study treatment causality, seriousness and severity) occurred with the same SOC and PT:

- a single occurrence will be counted if there is ≤ 1 day gap between the end date of the preceding AE and the start date of the consecutive AE
- more than one occurrence will be counted if there is > 1 day gap between the end date of the preceding AE and the start date of the consecutive AE.

For occurrence, the presence of at least one SAE / SAE suspected to be related to study treatment / non SAE has to be checked in a block e.g., among AE's in a ≤ 1 day gap block, if at least one SAE is occurring, then one occurrence is calculated for that SAE.

The number of deaths resulting from SAEs suspected to be related to study treatment and SAEs irrespective of study treatment relationship will be provided by SOC and PT.

Other safety evaluations

[figure not shown]
Anion gap

From measurements of sodium, chloride, and bicarbonate in serum, the anion gap in mmol/L will be derived as sodium – (chloride + bicarbonate) in mmol/L and will be an additional safety variable.

The anion gap and change from baseline in anion gap will be summarized by diabetic status, renal function, and day. Baseline will be derived from the Day 1 0-hour measurements. Summary statistics will include sample size, mean, standard deviation, minimum, median, and maximum.

For each subject, the maximum post-baseline value and the maximum change from baseline will be extracted and will be summarized by diabetic status and renal function. Summary statistics will include sample size, mean, standard deviation, 90% confidence interval, minimum, median, and maximum.

The frequency of patients with a maximum post-baseline value $< / \geq 11$ will be tabulated by diabetic status and renal function.

